5. SAFETY REPORTING

Temporary halt for reasons of subject safety

In accordance to section 10, subsection 4, of the WMO, the sponsor will suspend the study if there is sufficient ground that continuation of the study will jeopardize subject health or safety. The sponsor will notify the accredited METC without undue delay of a temporary halt including the reason for such an action. The study will be suspended pending a further positive decision by the accredited METC. The investigator will take care that all subjects are kept informed.

15. AEs, SAEs and SUSARs

5.5.1. Adverse events (AEs)

Adverse events are defined as any undesirable experience occurring to a subject during the study, whether or not considered related to a RMT device. All adverse events reported spontaneously by the subject or observed by the investigator or his staff will be recorded.

5.5.2. Serious adverse events (SAEs)

A serious adverse event is any untoward medical occurrence or effect that

- results in death;
- is life threatening (at the time of the event);
- requires hospitalisation or prolongation of existing inpatients' hospitalisation;
- results in persistent or significant disability or incapacity;
- is a congenital anomaly or birth defect; or
- any other important medical event that did not result in any of the outcomes listed above due to medical or surgical intervention but could have been based upon appropriate judgement by the investigator.

An elective hospital admission will not be considered as a serious adverse event.

The sponsor will report the SAEs to the accredited MREC that approved the protocol within 15 days after the sponsor has first knowledge of the serious adverse reactions. Only SAEs that occur within one month after the examinations at baseline and follow-up will be reported. SAEs that result in death or are life threatening should be reported expedited. The expedited reporting will occur not later than 7 days after the responsible investigator has first knowledge of the adverse reaction. This is for a preliminary report with another 8 days for completion of the report.

Evaluation of a Computerized Complex Instrumental Activities of Daily Living Marker (NMI) (AltoidaML)

All (S)AE's that occur within 24 hours of administration of the GE imaging agent, regardless of assessment of relatedness will be reported to GEHC. After this safety period of 24 hours, only adverse events that are considered related to the tracer will be reported to GEHC.

5.5.3. Follow-up of adverse events

All AEs will be followed until they have abated, or until a stable situation has been reached. Depending on the event, follow up may require additional tests or medical procedures as indicated, and/or referral to the general physician or a medical specialist.

SAEs need to be reported till end of study within the Netherlands, as defined in the protocol.

16. Data Safety Monitoring Board (DSMB) / Safety Committee

N/A

6. STATISTICAL ANALYSIS

Data obtained from RMTs will be either continuous (as, for example, accelerometer recording having several samples per second, participant's relative locations recorded via GPS every 5 minutes, ...) or obtained during a single clinical visit only (as, for example, gait assessment). Continuous raw data will be analytically processed and features characterizing behaviour per day will be obtained. For example, actigraphy read-outs will be used to derive sleep characteristics using Cole-Kripke algorithm (duration, quality of sleep, etc.) for every night, relative location data will be used to estimate distance travelled per day, duration of home stay per day, number of places visit per day and so on. Complete strategy for handling multi-sensor data and list of relevant features will be developed through the project duration. At the end, RMT data will be either a day-by-day time series or obtained at a single study time point.

We will analyse each RMT measurement separately, characterizing their variance to assess, whether 1) they are different between following groups: (a) healthy volunteers and (b) subjects with preclinical AD, (c) subjects with MCI due to AD, and (d) subjects with mild-to-moderate AD dementia, and 2) whether they are related to standard clinical questionnaires for ADL. For a continuous day-by-day time series, we will model such a RMT measure using a mixed-effect model for repeated measures (MMRM) based on observed case data. The model will include study group (or a related ADL scale), age, sex, and other related covariates/factors. Strength of between study groups difference (or relation to related ADL scale) is of primary interest. The within-participant covariance between visits will be estimated via an unstructured variance-covariance matrix. In case of convergence problems, alternative variance-covariance structures will be tried in the following order, with the first structure that converges being used in the analysis: heterogeneous Toeplitz, standard Toeplitz, and AR(1) with separate participant random effect. Weekdays and weekends time

Evaluation of a Computerized Complex Instrumental Activities of Daily Living Marker (NMI) (AltoidaML)

series will be analyzed separately. For the case of RMT assessed only once per study at clinical visit (as gait assessment), analysis of covariance (ANCOVA) will be conducted. Namely, an RMT will be used as a dependent variable, whereas study group (or related ADL scale), age, sex, and other related covariates/factors will be included in the model. Correction for multiple comparison will be considered for univariate RMT modeling.

As a second step, we will try to answer the question, whether combination of different RMT assessments contributes to either study group discrimination and/or is related to ADL scale in a multivariate predictive modeling approach. Results of univariate modeling (described above) will be considered as a filter-based feature selection, which informs us on what information to include into the model. Continuous RMT data will be aggregated (as mean, standard deviation, lagged autocorrelation, ... estimated using data from a whole 8-week experiment duration) for each participant. These preselected aggregated features in combination with preselected RMT measures obtained at a single study point will be used for modeling. Under assumption that data are missing at random, multiple imputation will be applied for covariates, where missingness is not drastically high. Multivariate prediction (of either study group or related ADL scale) models will be constructed and further variable selection, based on, for example, LASSO L1-regularization for (generalized) linear models, or different feature selection algorithms will be applied. Models' performance will be characterized through the cross-validation.

For the assessments, which will be primary done at the clinic and repeated at home (as, for example, experiments with the Altoida app), results will be compared using Bland Altman analysis to assess the agreement between two quantitative variables. Based on the result, recommendation regarding possibility to use home-based tests will be provided. To check, whether 'real-world' (at home) assessment is beneficial to the one done in the 'clinical environment', we will check, whether the predictive models (described above) using 'home' assessments have better predictive performance, than the ones, using 'clinical' assessments.

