| | | Smoking | Once | 5 | Life habits & AD risk factors |
|--|--|---------|------|---|-------------------------------|

Evaluation of a Computerized Complex Instrumental Activities of Daily Living Marker (NMI) (AltoidaML)

2. Study design

The study is a multicentre, observational, cross-sectional, digital assessment cohort study in subjects with preclinical AD, MCI due to AD, and mild-to-moderate AD dementia. It consists of two parts: the main study (tier 1), where the subjects are provided with wearable digital devices, and a sub-study (tier 2), in which technologies are installed in the subjects' home (see table 2 above). The duration of the main study for individual subjects is 5 years of data collection, while for the sub-study (tier 2) a similar period of data collection is expected, with a flexible time between the two studies for arranging home-device wiring. The sub-study will be performed on those volunteers whose home setting shows the necessary technical requirements (please see table 2 above for the Residential Movement Detector).

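### An unstructured covariance matrix over days, dropped only if it fails to converge, is singular for most 2- to 5-year RMT series and, without a small-sample correction, understates standard errors in an 8-week series

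*Combined protocol and SAP*

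**What the plan says.** The Statistical Analysis section of the combined protocol and SAP sets the model for daily RMT features: "For a continuous day-by-day time series, we will model such a RMT measure using a mixed-effect model for repeated measures (MMRM"), fitted to observed cases. Group enters with age, sex and other covariates; no group-by-day term is listed. The covariance rule follows: "The within-participant covariance between visits will be estimated via an unstructured variance-covariance matrix".

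The only way out of that rule is failure to fit: "In case of convergence problems, alternative variance-covariance structures will be tried in the following order", namely "heterogeneous Toeplitz, standard Toeplitz, and AR(1) with separate participant random effect", "with the first structure that converges being used in the analysis". No degrees-of-freedom method, small-sample correction or sandwich standard error is named. Weekday and weekend "series will be analyzed separately".

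The length of the series is not settled. The same section aggregates RMT data over an 8-week experiment. The Population section requires, as a rule of thumb, at least 2 years of data for a participant to enter the final analysis. The Study design section says: "The duration of the main study for individual subjects is 5 years of data collection".

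**The concern.** The covariance rule is worded for a handful of visits, where an unstructured matrix is a sensible default. Applied to a daily series, its dimension is the number of days. Two things then go wrong, depending on the length. If there are more days than participants, the matrix cannot be estimated. If there are fewer days, but not far fewer, it can be estimated and the fit may converge. The group effect is then a weighted average over days whose weights come from a noisy matrix, and the model-based standard error ignores that noise. Convergence says nothing about this, so the plan's safeguard does not catch it.

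This model gives the between-group comparison that the section calls its primary interest, for every daily RMT. The univariate results also inform which features enter the prediction models.

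**Working it through.** **The plan's own figure.** The plan gives no error rate for the MMRM, so there is none to reproduce. Its sample-size section gives 55 per group in four groups; 4 x 55 = 220 in total, although the text calls 220 a per-group number and 440 the total. Stated enrolment is 283 AD subjects plus 213 (Summary) or 215 (Population) controls, so 496 or 498. I use N = 220, 440 and 498.

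**Series lengths.** Weekdays and weekends are fitted separately:
- 8 weeks: 8 x 5 = 40 weekdays and 8 x 2 = 16 weekend days.
- 2 years (730 days): about 522 weekdays and 208 weekend days.
- 5 years (1,826 days): about 1,304 weekdays and 522 weekend days.

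**Covariance parameters.** Unstructured, T(T+1)/2:
- T=16: 136
- T=40: 40 x 41/2 = 820
- T=208: 21,736
- T=522: 136,503
- T=1,304: 850,860

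The fallbacks need 2T-1 (heterogeneous Toeplitz; 79 at T=40), T (Toeplitz; 40 at T=40) and 3 (AR(1) plus a participant effect).

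**Singularity.** An unrestricted T x T matrix estimated from N people has rank at most N. With N at most 498, it is singular for T of 522 or more: the 2-year weekday series and both 5-year series. The 2-year weekend series (208 days) can be fitted at N=498.

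**Standard errors where it can be fitted.** Take four groups, age and sex (six coefficients), complete data, a group effect constant over days, and model-based standard errors. Let c = (T-1)/(N-6). The estimated variance is too small by a factor of about 1-c and the true variance is inflated by about 1/(1-c). So model SE / true SE is about 1-c, and the two-sided false-positive rate is 2[1 - Phi(1.96(1-c))].

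| N | T | c | SE ratio | Formula | Simulated |
|---|---|---|---|---|---|
| 220 | 16 | 15/214 = 0.070 | 0.930 | 6.8% | 7.1% |
| 220 | 40 | 39/214 = 0.182 | 0.818 | 10.9% | 10.3-12.3% |
| 440 | 16 | 15/434 = 0.035 | 0.965 | 5.8% | 5.6-6.2% |
| 440 | 40 | 39/434 = 0.090 | 0.910 | 7.4% | 7.3-7.7% |
| 498 | 16 | 15/492 = 0.030 | 0.970 | 5.7% | 5.6-6.4% |
| 498 | 40 | 39/492 = 0.079 | 0.921 | 7.1% | 6.7-7.6% |
| 498 | 208 | 207/492 = 0.421 | 0.579 | 25.6% | 26.4% |

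The simulations had no group difference and used Wald tests of adjacent groups at 1.96, with and without day as a factor. There were 1,500 runs per cell (150 for T=208). The Monte Carlo standard error per contrast is at most about 0.7 points near 7% (square root of 0.07 x 0.93/1,500) and 3.6 points for T=208. The 10.3% came from data generated with AR(1) plus a participant effect, so the problem does not need an unusual true correlation. A 3-df Wald test of all groups at T=40 rejected in 16-18% of runs at N=220 and about 9% at N=498.

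**Comparator.** In the same runs, ANCOVA on each participant's mean over days rejected in 4.2-6.1%.

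**The case against.** The other side has several good points.

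- **The fallback chain exists.** A reader might infer that the plan has no usable model over 2 to 5 years. It does: where the matrix is singular, the chain ends in a three-parameter model close to what a statistician would choose for daily data. This stands. The damage there is confined to a first choice that cannot work, and to the 2-year weekend series, where it can be fitted but performs badly.
- **The size at planned enrolment is modest.** A reader might infer a false-positive rate near 15%. That needs one 56-day model and N=220 (formula: 14.5%). No 56-day model is planned, because weekdays and weekends are fitted separately, and 220 is under half the stated enrolment. N=220 remains a useful lower case, because the sample-size total is unclear and participants with under 2 years of data would be dropped.
- **The inflation depends on choices the plan leaves open.** With complete data, a group-by-day model averaged equally over days is the same test as the participant-mean ANCOVA. A first-order Kenward-Roger-type correction brought the simulated rate to about 5-7% for the 16- and 40-day fits. This stands as a condition on the figures. But the section lists group without a day interaction and names no correction, so a programmer following it gets the uncorrected result.
- **Convergence is assumed.** Whether an 820-parameter fit with missing days converges was not tested. If it does, missing days would probably make the standard errors worse, but this was not simulated.
- **The weekday/weekend split is legitimate.** A reader might infer that it corrupts the Toeplitz and AR(1) lags, since Saturday to Sunday and Sunday to the next Saturday could count as one step each. That holds only if days are indexed by order rather than date, and the plan states neither. Nor does using different structures for different RMTs by itself make p-values non-comparable, provided each structure is valid.

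**Conclusion.** The point holds as an error in a stated rule, not merely as missing detail. Unstructured-over-days is singular for most 2- to 5-year series, so it cannot serve as first choice there. The 2-year weekend series can be fitted at N=498, but with a false-positive rate of about 25%. For an 8-week series the rule requires the unstructured fit whenever it converges. For 40 weekdays, standard errors are then about 8% too small at N=498 and 18% at N=220, with per-contrast false-positive rates of about 7-8% and 10-12%. For 16 weekend days, standard errors are about 3% and 7% too small, and the rate is about 6-7%.

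These sizes rest on a group main effect without group-by-day interaction, model-based standard errors without a Kenward-Roger or similar correction, and complete data. Which case applies cannot be decided until the three series lengths are reconciled.

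**What to change.** First, reconcile the 8-week, 2-year and 5-year statements, and state the repeated unit and the number of repeats for each daily RMT. Then replace the unstructured-over-days rule with one of the following:

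1. Analyse one participant mean per pre-specified window. Use ANCOVA if there is one window. If there are a few, use MMRM with an unstructured matrix over windows and Kenward-Roger degrees of freedom.
2. Keep daily modelling, but name one parsimonious structure for all daily RMTs: a participant random effect plus serial correlation by calendar-day distance, with sandwich standard errors.

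Separate weekday and weekend analyses may stay; a single model with a group-by-weekend term is optional.

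The cost is SAP wording only, with no change to data collection. P-values will be slightly less favourable than under the present rule.

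### For daily RMT series, the step-one filter tests the mean level only, while the step-two model is built on mean, standard deviation and lagged autocorrelation

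*Combined protocol and SAP*

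**What the plan says.** All of this stands in section 6 (Statistical Analysis) of the combined protocol and SAP.

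- **Step one, daily series.** "we will model such a RMT measure using a mixed-effect model for repeated measures (MMRM) based on observed case data". On the terms: "The model will include study group (or a related ADL scale), age, sex, and other related covariates/factors". On the target: "Strength of between study groups difference (or relation to related ADL scale) is of primary interest". On the covariance: "The within-participant covariance between visits will be estimated via an unstructured variance-covariance matrix".
- **Step one, single-visit RMTs.** ANCOVA with the same kinds of terms, given only for RMTs assessed once at a clinic visit. Multiplicity correction is something to be considered; no method or level is given.
- **Link to step two.** "Results of univariate modeling (described above) will be considered as a filter-based feature selection". The sentence goes on to say that these results inform the choice of what enters the model. No pass threshold is stated.
- **Step two.** "Continuous RMT data will be aggregated (as mean, standard deviation, lagged autocorrelation", from an eight-week recording period. Then: "These preselected aggregated features in combination with preselected RMT measures obtained at a single study point will be used for modeling". Further selection, for example by LASSO, and cross-validation follow.

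**The concern.** A filter is useful if it tests the quantity that the later model will use. Here the group or ADL term in the MMRM compares mean daily levels. The plan describes one within-participant covariance structure, with no group-specific covariance and no test of it. ANCOVA is not assigned to daily series. So of the three aggregates named for step two, only the mean is screened by a test of itself.

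A series can have the same average level in every group and still be more erratic, or less correlated from day to day, in one of them. A mean-level screen cannot see that, and LASSO cannot recover a feature that it never receives. This is a separate matter from whether the filter sits inside the cross-validation: a correctly nested filter would still test the mean.

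At stake is the step-two answer on whether combined RMT features separate the stages or relate to ADL. Section 6 also judges the value of home assessment by comparing the predictive performance of home and clinic models. A measure taken at a single clinic visit has no day-to-day SD or autocorrelation, so this particular loss can fall only on the daily data.

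**Working it through.** **No plan figure to reproduce.** The plan gives no operating characteristics for the filter. The 55 per group in the sample size section is used below only as a group size. It cannot be re-derived, because its SDs come from a figure in a cited paper.

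**Inputs from the plan.** 55 per group; 8 weeks × 7 = 56 daily values.

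**Assumed, because the plan is silent.** Filter alpha 0.05 two-sided; between-person SD of the level 1; day-to-day SD 1 in the reference group; lag-1 autocorrelation φ = 0.3; complete data. Person-to-person variation h in the log of the day-to-day SD is taken as 0.25 or 0.50 (about 25% or 50%).

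**Mean-level screen.** With complete data, a test on participant means stands in for the MMRM group effect. If the group means are equal, the null hypothesis being tested is true whatever the day-to-day SDs are. The pass rate is therefore about alpha, 5%, and a larger sample does not raise it. Simulation gives about 5% at each SD ratio tried.

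**Screen on the SD feature.** Compare log SD between two groups.
- Sampling variance of one person's log SD ≈ [1/(2 × 56)] × (1 + φ²)/(1 − φ²) = (1/112) × (1.09/0.91) = 0.0107.
- Spread of log SD between people = √(h² + 0.0107), which is 0.271 for h = 0.25 and 0.511 for h = 0.50.
- Noncentrality = [ln(ratio)/spread] × √(55/2), with √27.5 = 5.244.
- Power ≈ Φ(noncentrality − 1.98).

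| SD ratio | ln(ratio) | h | Noncentrality | Power by formula | Simulation |
|---|---|---|---|---|---|
| 1.15 | 0.140 | 0.25 | 2.71 | 77% | about 76% |
| 1.25 | 0.223 | 0.25 | 4.32 | 99% | about 99% |
| 1.15 | 0.140 | 0.50 | 1.44 | 29% | about 28% |
| 1.25 | 0.223 | 0.50 | 2.29 | 62% | about 63% |

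**Autocorrelation.** In a four-group simulation with equal means and SDs and lag-1 autocorrelation 0.30/0.25/0.20/0.15 by stage, the mean screen passes 5.3% of runs. A test on the autocorrelation feature passes 99.8%.

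**If the means also differ.** Two groups, SD ratio 1.25, h = 0.25: at mean differences of 0.1, 0.2 and 0.3 between-person SD, the mean screen passes about 8%, 18% and 34%. At 0.5 it passes about 70%. Four groups with an overall test, control and preclinical means equal, later stages shifted by 0.25 and 0.5 SD: about 70% pass. With shifts of 0.3 and 0.6 SD, about 87% pass.

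**Weekday and weekend series.** The plan analyses these separately. If either could admit the RMT and the two tests were independent, the chance pass rate would be at most 1 − 0.95² = 9.75%, still far below the SD-feature rates above.

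**The case against.** The strongest reply is that the plan never says an RMT is dropped. The filter informs the choice, no threshold is written, and the phrase about preselected aggregated features could mean that the aggregates themselves are screened. That stands: exclusion is an inference from the ordinary meaning of a filter followed by further selection. It does not remove the gap, because on either reading no univariate test of SD or autocorrelation is described.

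Second, step one opens with "We will analyse each RMT measurement separately, characterizing their variance to assess, whether" and the list of daily features is left open. Some irregularity may therefore be captured in a daily value, such as sleep quality per night, whose mean is then tested. This is fair as far as it goes. But no model or test of variability is attached to the opening phrase, and SD and autocorrelation across days are formed only in step two.

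Third, a reader might infer that the loss is greatest for early contrasts such as control versus preclinical AD. The documents do not support that. They do not say that each pairwise contrast is filtered separately, and they expect impairment to rise with stage. An RMT whose mean moves only in MCI or dementia could pass and bring its SD and autocorrelation into every contrast. There is also the alternative ADL route into the model.

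Fourth, the effect sizes are assumptions, and the detection rate depends strongly on how much people differ in their own day-to-day SD. That is correct, and the table shows both values.

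**Conclusion.** The mismatch is real and limited. The only step-one model given for daily series tests the mean, and its results serve as the filter for a model that also uses SD and autocorrelation. The consequence follows if the filter is applied in the ordinary way and the RMT has little mean difference at any stage and no ADL relation in level. Such an RMT passes at about alpha (about 5% in the illustration), although its SD feature could be detected in 28% to 99% of studies over the assumed range. Step two could then understate what daily RMT data offer, including in the home-versus-clinic comparison.

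It would go too far to say that every RMT with a variability signal is discarded, or that 95% are lost. That figure needs equal means across all stages, and the documents do not show that any RMT behaves so. The primary between-group comparison is made in step one and is not affected.

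**What to change.** In section 6, reverse the order for daily series. Compute the participant-level aggregates first. Then screen each one (mean, SD, autocorrelation and any other) separately with the ANCOVA already specified for single-visit RMTs: study group or ADL scale, age, sex and other covariates. Run the screen inside each training fold of the cross-validation. Keep the MMRM for inference on level, and do not use it to screen SD or autocorrelation. State that each aggregate enters or leaves on its own result.

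The change takes a few sentences and no new data. The cost is several times more univariate screens per daily RMT: at least three, since the list of aggregates is open-ended. A reader might assume that the existing multiplicity correction absorbs this, but the plan only says correction will be considered. The amendment therefore has to name the screening threshold or the multiplicity rule.

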2. OBJECTIVES & OUTCOMES

1. Objectives

The main objective is to assess the performance of selected RMTs against ADL standard clinical questionnaires in finding differences among individuals of various classes of severity of AD and investigate if RMT measurements are more precise and better reflect disease progression and functional /QoL changes compared to ADL standard measurements.

Secondary objectives:

- to assess associations between RMT measurements and standard clinical scales used to assess specific clinical conditions and functional impairments in AD patients;
- to assess if RMT measurements are more precise and more ecological;
- to investigate the patient acceptability and user-friendliness of selected RMTs;
- to assess the technical performance of RMTs in a real-life setting.
- to assess associations between RMT measurements, standard clinical scales and AD-related biomarker in blood and CSF
- to explore new AD-related biomarkers.

To achieve the non-invasive aspect of these objectives, measurements will be performed in clinic (i.e. under supervision of a clinical team) and in non-clinical, real life settings (i.e. at home, at work, etc.).

Primary Outcome

- Difference between healthy controls, subjects with preclinical AD, subjects with MCI due to AD, and subjects with mild-to-moderate AD dementia using selected RMTs measurements aimed to profile ADL, using diagnostic criteria as defined under 3.1.3" Both primary and secondary outcomes.

¹ Buegler, M, Harms, RL, Balasa, M, et al. Digital biomarker-based individualized prognosis for people at risk of dementia. *Alzheimer's Dement*. 2020; 12:e12073. <https://doi.org/10.1002/dad2.12073>

Evaluation of a Computerized Complex Instrumental Activities of Daily Living Marker (NMI) (AltoidaML)

Secondary Outcomes

- Established clinical measures: difference between healthy volunteers, subjects with preclinical AD, subjects with MCI due to AD, and subjects with mild-to-moderate AD dementia in the following assessments of specific functions when performed in the clinic (in brackets, it is indicated which functional domain and/or main outcome measure is covered by the assessment):
 - Amsterdam-iADL
 - (orientation, planning skills & memory required for task completion household management).
 - ADCS-ADL
 - (orientation, planning skills & memory required for task completion household management).
 - CERAD neuropsychological test battery

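### The check on whether home assessment beats clinic assessment has no criterion for chance: read literally, a higher cross-validated score is enough

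*Combined protocol and SAP*

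**What the plan says.** The last part of Section 6 (Statistical Analysis) sets out to check "whether 'real-world' (at home) assessment is beneficial to the one done in the 'clinical environment". The means is to see whether the "predictive models (described above) using 'home' assessments have better predictive performance, than the ones, using 'clinical' assessments". How performance is measured is covered by one sentence: "Models' performance will be characterized through the cross-validation".

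The models come from the second analysis step: "Multivariate prediction (of either study group or related ADL scale) models will be constructed". Their inputs are pre-selected: "Results of univariate modeling (described above) will be considered as a filter-based feature selection". The plan does not say whether that filter is run inside the cross-validation folds. On multiplicity it says only: "Correction for multiple comparison will be considered for univariate RMT modeling".

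The related secondary objective in Section 2 is "to assess if RMT measurements are more precise and more ecological".

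Nothing else supplies a criterion for better:
- The Bland-Altman analysis in Section 6 concerns agreement between settings.
- The ecological-value outcome in Section 2 is an association between clinic and real-life measurements.
- The only stated significance level, 0.05 with Holm adjustment under Sample size calculation, covers three adjacent-group contrasts on the Amsterdam IADL.

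**The concern.** Two cross-validated scores from the same participants will almost never be equal. Without an interval, test or margin, one setting will always come out ahead, and the plan gives no means of telling a real advantage from chance. Who wins may also depend on how many candidate features each setting supplies and where the filter sits, rather than on the information in the assessments.

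At stake is a published statement that home assessment predicts stage or function better than clinic assessment. This is the only planned analysis that asks that question.

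**Working it through.** **Stated figure.** The documents give no error rate, margin or expected difference for this comparison, so there is nothing on the point to reproduce. The nearby design figure (55 per group, 80% power) uses interquartile ranges from a figure in a cited paper and cannot be rebuilt from the documents. If the three steps are assumed equal, simulated power is 0.77 at 0.65 SD per step and 0.85 at 0.70 SD. Interpolating, 0.65 + 0.05 × (0.80 − 0.77)/(0.85 − 0.77) ≈ 0.67 SD, which motivates the d = 0.665 used below.

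**Inputs.** Sizes come from the documents: 55 per group and 220 (Sample size calculation, where 220 is four times 55 but is also called a per-group number), and 283 AD subjects with 213 or 215 controls (Summary; Study Population). Assumed: AUC as metric, a ridge-type linear classifier, the number of features, effect sizes and home-clinic correlation.

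**1. The literal rule.** Let D = performance(home) − performance(clinic), and claim a benefit if D > 0. If the two feature sets are like for like and equally informative, D and −D have the same distribution. Then Pr(D > 0) = [1 − Pr(D = 0)]/2 ≈ 0.5 at any sample size.

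| Simulation, equal information | Size | Home higher |
|---|---|---|
| 5 features per setting, correlation 0.5, d = 0.665 or 0.3 in both, 5-fold | 55 v 55 | 50–52% |
| 5 informative features per setting, effect 0.10 or 0.25 SD, correlation 0, 0.5 or 0.8, 10-fold; 12 scenarios, 1000 runs each | 55 v 55 and 283 v 213 | 48.5–51.4% |
| Further re-runs | 55 v 55, 215 v 283, 220 v 220 | 47–52% |

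**2. Size of a chance lead.** Pr(D > 0.03) ≈ 1 − Φ(0.03/SD).
- 55 v 55: SD 0.085–0.098 gives 1 − Φ(0.35) = 36% to 1 − Φ(0.31) = 38%. Simulated values over the runs were roughly 32–38%.
- 220 v 220 and 283 v 213: SD about 0.03 gives 1 − Φ(1.0) = 16%. Simulated values at these sizes and at 215 v 283 were roughly 12–20%.
- The 12-scenario grid had SD 0.023–0.052 at 283 v 213, which by the same formula spans 9–28%. The larger-sample figure therefore depends on the assumed effect and correlation.

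**3. Unequal numbers of candidate features.** Information was kept equal, with 50 v 10, 100 v 20 or 200 v 20 home and clinic candidates.
- Filter run on all data first: home higher in 82–99%, and 77–93% in a re-run. The filter has already seen the test-fold outcomes, and the larger pool gains more from that.
- Filter inside the folds: 21–36%, and 22–26% in a re-run. The larger pool now costs performance because more noise is selected.

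**4. A paired interval.** Over J fold-wise differences with mean D̄ and standard deviation s, the corrected resampled t-test uses SE = s × √(1/J + n_test/n_train). For eight repeats of 5-fold at 55 v 55, J = 40 and n_test/n_train = 22/88 = 0.25. The factor is 0.025 + 0.25 = 0.275 against 0.025 uncorrected, so the SE is √11 ≈ 3.3 times larger.
- Like-for-like null: the lower limit exceeded 0 in 3.5–4.0%, 2–5% and about 2% in three separate sets of runs (nominal 2.5%).
- Clear advantage (d = 1.0 v 0.3, 55 v 55): detected in 81–90%.
- Filter left outside the folds, unequal candidates, null: the interval still excluded 0 in 6% in one set of runs and 20–38% in another.
- Simpler tests: DeLong on cross-validated predictions gave 3.9–9.8%. Bootstrapping out-of-fold scores, in a separate 300-trial run with single 5-fold cross-validation, gave 4.7% and 10.3%.

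**The case against.** The plan is silent rather than wrong. It does not say that point estimates alone will be compared, and a competent analyst might attach an interval. That stands: a reader might infer that the plan prescribes a bare comparison of two scores, but the documents show only that no decision rule is given and that, on a literal reading, a higher score meets the criterion.

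The 50% is a symmetry result. It fits assessments repeated in both settings, such as the Altoida app. Elsewhere Section 6 sets aggregates of continuous home data beside single-visit measures, where feature counts can differ. This also stands. It limits the 50% but does not rescue the rule, since the rate then moves well above or below one half for reasons unrelated to information.

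The plan's recommendation on home testing rests on Bland-Altman, the ecological objective has its own association outcome, and this check closes an exploratory second step. All true, and it lowers the importance. Neither of those analyses asks which setting predicts better, so the gap remains.

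**Conclusion.** The point holds as a recommended change to a secondary analysis. For like-for-like assessments with equal information, the literal criterion favours home about half the time at every size examined. With unequal candidate counts the rate was about 77–99% or 21–36%, depending on where the filter sits. These figures rest on the assumed metric, classifier, effects and correlations; only the 50% follows from symmetry alone.

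Stronger readings that the documents do not support:
- **A one-in-five chance of preferring home when it is truly worse.** This is 18–23% at 55 v 55 with d = 0.45 v 0.665, and about 1–2% at 215–220 or more per arm. Neither d is in the documents.
- **A 75% chance of at least one home win over two targets.** 1 − 0.5² = 75% needs independent targets. With correlation ρ it is 1 − [1/4 + arcsin(ρ)/(2π)], or 67% at ρ = 0.5 and 60% at ρ = 0.8. Section 1 assumes that disability rises with stage, so independence is implausible.
- **That the comparison is central to the study.** The main objective in Section 2 sets RMTs against standard ADL questionnaires.

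**What to change.** Replace the home-clinic check in Section 6 with text to this effect:

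- Home and clinic models are fitted on the same participants and the same outer folds of a repeated cross-validation.
- All feature selection (including the univariate filter), imputation and tuning are done within the training folds.
- One performance metric and one deciding target are named in advance; any other target is supportive. If study group is chosen, MMSE and CDR should not be predictors, because the inclusion criteria use them to define the groups.
- The paired difference is reported with a 95% confidence interval from the corrected resampled t-test, with variance factor 1/J + n_test/n_train, where J is the number of folds over all repeats.
- Home is called beneficial only if the lower limit exceeds 0. Otherwise the result is reported as inconclusive, with its interval.
- The interval is stated to be approximate: about 2–5% one-sided false claims in simulation against a nominal 2.5%.

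The cost is a few sentences and some computing time, with no new data. The downside is that modest true advantages will be reported as inconclusive.
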